3.4. Test meals composition

All test meals were matched for energy, LGI-Milk and LGI-Kefir meals also for macronutrients and GI, but HGI-Kefir meal had a nearly 2-fold difference in GI (Table 1). Furthermore, both milk and kefir drinks contained 120mg/100ml calcium, and kefir drink also had 107 CFU/g

probiotic bacteria (*Lactobacillus* spp. and *Streptococcus* spp.). The energy content of test meals (~445 kcal) were estimated as corresponding to about 25% daily energy needs of a sedentary female (Chowdhury, et al., 2015), and the daily energy needs were also calculated by the Schofield equation, taking into account: gender, age, weight and a physical activity level of 1.3.

Table 1. Nutritional composition and glycaemic index of the component foods in test meals

	Portion size (g/ml)	Energy (kJ[kcal])	AvCHO* (g)	Protein (g)	Fat (g)	GI (%)
LGI-Milk						
Milk (full-fat)	200	524(125)	9.9	5.8	6.8	31
Cheddar cheese	25	424(101)	0.0	6.4	8.5	0
Apple	200	469(112)	24.9	0.9	0.9	36
Grain bread	50	435(105)	19.1	4.8	0.9	50
Toplam		1852(443)	53.9	17.9	17.1	40
LGI- Kefir						
Kefir (full-fat, plain)	200	526(126)	10.0	5.8	6.3	36
Cheddar cheese	25	424(101)	0.0	6.4	8.5	0
Apple	200	469(112)	24.9	0.9	0.9	36
Grain bread	50	435(105)	19.1	4.8	0.9	50
Toplam		1854(444)	54.0	17.9	16.6	41
HGI- Kefir						
Kefir (full-fat, plain)	200	526(126)	10.0	5.8	6.3	36
Raspberry jam	50	568(136)	31.8	1.7	0.0	78
White bread	75	773(185)	34.0	7.0	1.5	70
Toplam		1868(447)	75.8	14.5	7.9	70

*AvCHO, available carbohydrate including sugars and starch, excluding fiber.

GI of foods in test meals was estimated by using the GI tables, with glucose as the reference food (Bao, Atkinson, Petocz, Willett, & Brand-Miller, 2011). The average meal GI was calculated as follows:

$$\text{Meal GI} = \frac{\sum_{a=1}^N (\text{GI}_a \times \text{AvCHO}_a \times \text{Frequency}_a)}{\sum_{a=1}^N (\text{AvCHO}_a \times \text{Frequency}_a)}$$

where n is the number of foods consumed, GI_a is the GI for food a, AvCHO_a is the available carbohydrate content per serving of food a, and Frequency_a is the consumption frequency of one serving of food a during the meal.

3.5. *At libitum lunch*

At 180 min after the test breakfast, participants were presented with the ad libitum lunch following appetite measurements. Frequently consumed foods were used to prepare the lunch consisting of pasta with tomato sauce, yogurt drink and mandarin. Participants were asked to

consume whatever they wanted and to eat until they felt comfortably full. Foods were weighed or measured to the nearest 0.1 g before consumption, and any remaining food was reweighed to determine intake at lunch. Energy and macronutrient values were calculated using The National Food Composition Database (TurKomp), and manufacturer labelling.

3.6. Assessment of appetite sensations

Subjective assessment of appetite sensations was performed by using a visual analogue scale (VAS) composed of lines (of 100 mm in length) with words anchored at each end, expressing the most positive and the most negative rating. VAS was used to assess appetite scores (hunger, fullness, desire to eat, and prospective food consumption), desire for specific food types (sweet, salty, savoury, and fatty) and the palatability of test meals (visual appeal, smell, taste, after taste, and overall palatability) (Flint, Raben, Blundell, & Astrup, 2000). A series of VAS were administered using the paper-and-pen method at specific time-points during the examination period. Participants were asked to make a single vertical mark at the appropriate point between the 2 anchors on each scale corresponding to their feelings. A new VAS booklet was provided to participants for each rating time, and nobody could compare to his/her previous ratings when marking the VAS. Appetite scores were quantified by measuring the distance in millimetres between the left end of each line and the mark. Furthermore, the separate VAS components such as hunger, fullness, desire to eat and prospective food consumption were combined to produce an additional measure termed 'composite appetite score'. This validated average appetite score was calculated for each time point using the following equation: [(hunger + desire to eat + prospective food consumption + (100 - fullness))/4] (Leidy, et al., 2015).

4. Statistical Analysis Plan

4.1. Sample size

A power-based sample size calculation based on previous research from Stevenson et al. (Stevenson, Astbury, Simpson, Taylor, & Macdonald, 2009) revealed that 21 participants were needed to provide 80% power to detect 5% difference between groups in primary outcomes. To allow discontinuation during the study, 24 participants (considering 15% losses) were recruited, and the study was concluded with 22 participants.

4.2. Data analysis

Statistical analysis was performed using the Statistical Package for the Social Sciences (version 22.0; IBM SPSS Statistics) software. Data were expressed as the mean \pm SD unless otherwise indicated. Normality was assessed using the histogram and normal Q-Q plots, and also Shapiro-Wilk test. Furthermore, continuous variables were examined for skewness and kurtosis, and log-transformed before analysis and reported back-transformed geometric means (G) \pm standard error (S.E) when required (Akin, et al., 2015). Postprandial appetite sensations were quantified as area under the curve (AUC) calculated according to the trapezoidal rule. One-way (1-factor) analysis of variance (ANOVA) for repeated measures was applied to determine statistical differences between groups. In addition, the data were analysed by using 2-factor (time x meal) repeated-measures ANOVA, and Bonferroni post hoc tests were applied to significant time x

meal interactions. For all statistical analyses, p values less than 0.05 were considered to have statistical significance.

REFERENCES

Chang, K. T., Lampe, J. W., Schwarz, Y., Breymeyer, K. L., Noar, K. A., Song, X., & Neuhouser, M. L. (2012). Low glycemic load experimental diet more satiating than high glycemic load diet. *Nutr Cancer*, 64, 666-673.

Chowdhury, E. A., Richardson, J. D., Tsintzas, K., Thompson, D., & Betts, J. A. (2015). Carbohydrate-rich breakfast attenuates glycaemic, insulinaemic and ghrelin response to ad libitum lunch relative to morning fasting in lean adults. *Br J Nutr*, 114, 98-107.

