3.3. Study design

This was a randomized, single-blind, 3-intervention crossover trial conducted on 3 separate days, with a 1-week washout period between each study day. All participants were randomly submitted to three different test meals with the following different GI amounts and milk or kefir: a low-GI and milk content (LGI-Milk), a low-GI and kefir content (LGI-Kefir), and a high-GI and kefir content (HGI-Kefir). The order of the test meals was determined by using a computer-generated randomization sequence before recruitment. The primary outcomes were appetite sensations and subsequent food intake. Desire for specific food types and palatability of test meals were the secondary outcomes.

Participants received each test meal in a randomly assigned order on three different mornings separated by a washout period of 1-week when they were asked to maintain their usual diet and physical activity. On the day before each test meal, participants were instructed to eat a standard evening meal at 21:00 h and to refrain from eating and/or drinking (except for water) and/or doing any physical activity beyond that of their typical daily activities. Moreover, participants were tested within the follicular phase of their menstrual cycle (3–10 d after onset of menses) to avoid possible influences of menstrual cycle phase on hormonal changes and appetite (Chowdhury, Richardson, Tsintzas, Thompson, & Betts, 2015).

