On the each testing day, participants arrived in the testing room at 08.30 h following a 12-h fast and anthropometric measurements were completed before eating the test meal. Also, first appetite scores were measured for baseline measurements (time zero). At 09:00 h participants received the test meal blinded to its nutritional characteristics and were asked to consume within 15 min. During the postprandial period, participants remained at rest in the testing room and appetite scale was applied at 15, 30, 60, 90, 120, 150 and 180 min. Moreover, participants were asked to assess the palatability of test meal at 15 min (immediately after consuming test meal). No food or drink other than water was allowed following consumption of the test meal until an ad libitum lunch. Water was available ad libitum throughout the first trial; however, the volume consumed was measured and the participants drank the same volume during the second and third trial. Participants were permitted to watch movies, read, or play with electronic devices (laptop computer, mobile phone etc.) or undertake other similar sedentary activities throughout each test day but were not allowed to sleep.

This study was conducted according to the guidelines laid down in the Declaration of Helsinki. All procedures were approved by the Clinical Research Ethics Committee of the Erciyes University (2016/547) on 21 October 2016, and all participants gave written informed consent. In addition, it was registered at ClinicalTrials.gov as NCT03636217.

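### Neither stated ANOVA has a visit (period) term for this randomised three-visit crossover; a visit-adjusted sensitivity analysis is a cheap safeguard for precision

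*Combined protocol and SAP*

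**What the plan says.** Section 3.3 describes a three-meal crossover: "Participants received each test meal in a randomly assigned order on three different mornings separated by a washout period of 1-week". On allocation it says only that "The order of the test meals was determined by using a computer-generated randomization sequence before recruitment". It does not say whether the orders were balanced over visits. It also says that "The primary outcomes were appetite sensations and subsequent food intake".

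Section 4.2 states two inferential models. In the first, "One-way (1-factor) analysis of variance (ANOVA) for repeated measures was applied to determine statistical differences between groups"; the only factor is meal. In the second, "the data were analysed by using 2-factor (time x meal) repeated-measures ANOVA", with Bonferroni post hoc tests after a significant interaction. Section 3.3 gives the ratings to which time refers: after a baseline score, the "appetite scale was applied at 15, 30, 60, 90, 120, 150 and 180 min". Time is therefore minutes within a test day, not visit number. No visit, period or sequence term is mentioned anywhere.

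On numbers, section 4.1 reports that "24 participants (considering 15% losses) were recruited, and the study was concluded with 22 participants", against 21 needed for 80% power.

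**The concern.** In a crossover, each response carries a meal effect and a visit effect. A model without visit leaves any visit effect in the within-person error. That widens the standard error of the meal contrasts and lowers power for the primary outcomes. If meals are unevenly spread over visits, part of the visit effect also enters the realised meal contrast.

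A visit effect is plausible here. Section 3.3 treats visit 1 differently by design: water is freely available at the first visit, and the volume drunk there is repeated at the second and third. Self-rated scales are also applied in the same way three times. With 22 analysed against 21 required there is little slack, and a null kefir-versus-milk result is less informative if visit variation sits in the error term.

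**Working it through.** **The plan's own figure.** The 21 in section 4.1 cannot be reproduced, because no SD, correlation or test is given. Read as a two-sided paired t-test at 0.05 (an assumption), 21 participants and 80% power imply a standardised difference of 0.643. A 5% difference then implies an SD of differences of 5/0.643 = 7.8%, and a within-person SD of 7.8/√2 = 5.5%.

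**Inputs.** From the documents: n = 22, 3 meals, 3 visits, alpha 0.05 (taken as two-sided). Assumed: a linear drift R from visit 1 to visit 3, in within-person SDs, and a meal effect giving 80% power without drift. That effect is 0.970 SD between the outer meals for the overall test, with the third meal midway, or 0.865 SD for one pairwise contrast.

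**Degrees of freedom.** Without visit: (22 - 1) x (3 - 1) = 42. With visit: 42 - 2 = 40.

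**Closed form, balanced orders.** Visit effects are -R/2, 0 and R/2, with sum of squares R²/2. Leaving them out multiplies the error mean square by 1 + 22 x (R²/2)/42, which is 1.065 at R = 0.5 and 1.262 at R = 1. The contrast SE, √(2/22 x factor), goes from 0.302 to 0.311 and 0.339. The overall test has noncentrality 22 x 0.970²/2 = 10.35. Dividing by the factor gives 9.71 and 8.20. Power on 2 and 42 df is 80.0%, 77.3% and 69.6% at R = 0, 0.5 and 1; with visit, on 2 and 40 df, it is 79.8% throughout.

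**Simulation** (40,000 runs per setting; power without / with visit, %). Balanced means 24 participants over six orders with two lost at random. Unrestricted means each order drawn independently.

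| Drift R (SD) | Overall, balanced | Overall, unrestricted | Pairwise, balanced | Pairwise, unrestricted |
|---|---|---|---|---|
| 0 | 80 / 79 | 80 / 78 | 80 / 80 | 80 / 78 |
| 0.25 | 79 / 79 | 79 / 78 | 79 / 79 | 79 / 78 |
| 0.5 | 77 / 79 | 77 / 78 | 78 / 80 | 77 / 77 |
| 0.75 | 75 / 80 | 74 / 78 | 76 / 80 | 74 / 78 |
| 1.0 | 71 / 80 | 70 / 78 | 72 / 80 | 71 / 78 |

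The pairwise columns are unadjusted contrasts, which section 4.2 does not itself state. Before rounding, the cost at R = 0 is 0.2 to 0.3 points if balanced and 1.9 to 2.4 if unrestricted.

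**Type I error of the overall test without visit.** With unrestricted orders it stays at about 5%. With balanced orders it falls to about 2.5% at R = 1, so the test is conservative. With visit in the model it is about 5% in both cases.

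**Leak into a meal contrast at R = 1.** For balanced orders with two lost, all 276 possible losses were enumerated: mean 0.03 SD, maximum 0.09. For unrestricted orders, the visit difference between two meals is ±0.5 in four of the six orders and ±1 in two. Its variance per participant is (4 x 0.25 + 2 x 1)/6 = 0.5, so the SD of the mean is √(0.5/22) = 0.151. Simulation gives a mean absolute leak of 0.12 and a 95th percentile of 0.30, against an SE of about 0.30. At R = 0.5 the leak is half of that.

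**Where a visit shift cancels.** A shift that is constant over a visit's ratings moves that visit's mean but not the shape of its curve. In one simulated data set (22 participants, 3 meals, 8 rating times), adding a visit shift of 1.0 left the interaction F at 0.922 and moved the meal main-effect F from 1.05 to 2.45. The same shift cancels from an AUC measured from the time-zero score, but not from a total AUC.

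**The case against.** The strongest reply is that the point is optional. The text is in the past tense and 22 participants have been assessed, so no design power is left to protect. The 7 to 9 point gain needs a drift of 1 SD. On the section 4.1 reading above, that is about 5.5%, more than the 5% difference the trial was sized for. If orders were unrestricted and there is no drift, the term loses about 2 points. Choosing a model after the data exist, over several appetite scores and lunch intake, adds analytic flexibility.

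Much of this stands. The benefit is conditional, and the documents size neither the drift nor the balance of orders. The flexibility argument is a good reason not to replace the stated analysis. What does not stand is that the past tense removes the benefit: a re-run on existing data can still tighten the meal contrasts, and its cost is small and known.

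The AUC also needs a qualification. Section 4.2 gives only the trapezoidal rule, without saying whether the AUC is total or baseline-subtracted. In the second case a constant visit shift is already removed.

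A reader might infer that the omission biases the meal comparison or produces false positives. Randomised order rules out bias on average, and the simulated type I error is at or below about 5%.

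**Conclusion.** The gap is real and concerns precision. Neither stated model contains visit. At n = 22, adding it changes power by about 0 (balanced) or -2 points (unrestricted) with no drift, by +2 or about 0 to +1 at 0.5 SD, and by +8 to +9 or +7 to +8 at 1 SD. These figures rest on an assumed linear drift and an assumed meal effect, since the documents give neither a within-person SD nor a visit effect.

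The point applies to lunch intake, to a total AUC and to the meal main effect of the time x meal model. It would be tempting to extend it to the time x meal interaction, but a constant shift cancels there; only a visit effect that varies over the rating times would matter. Nor do the documents support a claim that any conclusion of the trial is wrong.

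One neighbouring matter belongs in a separate point. Section 3.3 says that "participants were tested within the follicular phase of their menstrual cycle (3–10 d after onset of menses", yet three visits with 1-week washouts span at least 14 days. Those two statements must be reconciled, but the case for a visit term does not depend on how.

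**What to change.** - For lunch intake and each appetite AUC, fit meal and visit (1 to 3) as fixed effects with participant as random. Report within-person meal contrasts with 95% CI, as ratios where the variable was log-transformed. State whether the AUC is total or baseline-subtracted.
- For the meal main effect of the time x meal model, fit the same model to each visit's mean rating. If individual ratings are modelled instead, include a participant-by-visit random term. With participant alone random, a simulated null meal effect was rejected 18%, 41% and 58% of the time when 10%, 30% and 50% of the within-person variance was assumed to lie at day level. Leave the interaction test as stated.
- Because the data already exist, keep the stated ANOVA as the governing analysis and report the visit-adjusted result beside it as a named sensitivity analysis.
- State whether orders were balanced, and report the number analysed per meal order. A sequence term is optional; with 22 complete participants it leaves the meal contrasts unchanged.

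The cost is some SAP wording and a re-run in the same SPSS package. It uses two error degrees of freedom: about 0.3 power points if orders were balanced and about 2 if unrestricted, when there is no visit effect.

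### Section 4.2 compares the appetite AUC between meals without adjusting for the time-zero score taken at every visit, which may lose precision on a primary outcome

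*Combined protocol and SAP*

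**What the plan says.** Section 3.3 of the combined protocol and SAP states: "The primary outcomes were appetite sensations and subsequent food intake". On each test day, after an overnight fast and before the meal, "first appetite scores were measured for baseline measurements (time zero"; after the meal the "appetite scale was applied at 15, 30, 60, 90, 120, 150 and 180 min". The same section standardises the run-in to each visit: "participants were instructed to eat a standard evening meal at 21:00 h", with activity restricted and testing confined to one phase of the menstrual cycle.

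Section 4.2 says: "Postprandial appetite sensations were quantified as area under the curve (AUC) calculated according to the trapezoidal rule". The next sentence reads: "One-way (1-factor) analysis of variance (ANOVA) for repeated measures was applied to determine statistical differences between groups". A two-factor time-by-meal repeated-measures ANOVA is then added, and "Bonferroni post hoc tests were applied to significant time x" meal interactions. No covariate, ANCOVA, mixed model or change from baseline appears anywhere. The plan does not say whether the AUC is total or baseline-subtracted, or whether time zero is a level of the time factor.

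Section 4.1 gives the target: "21 participants were needed to provide 80% power to detect 5% difference between groups in primary outcomes". No SD or within-person correlation is given. The study ended with 22 women.

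**The concern.** A three-period crossover compares each woman with herself, so stable differences in appetite between women drop out. Differences between her own visits do not. If she arrives hungrier on one morning and this raises the whole curve, the AUC for that meal moves for a reason unrelated to the meal. The time-zero score measures that shift and precedes the meal, so it is a legitimate covariate, yet the AUC comparison as planned does not use it.

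Meal order is randomised, so the shift is noise rather than bias. What is at stake is the width of the interval and the power for one of two primary outcomes, in a small trial aiming at a 5% difference. Food intake and the time-by-meal interaction test are not affected by this point.

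**Working it through.** **Inputs.** From the documents: 80% power, 21 participants needed, 22 analysed, three meals, significance level 0.05, ratings at 0, 15, 30, 60, 90, 120, 150 and 180 min. Assumed: two-sided testing; equal variances and correlations across meals; r between 0 and 0.6.

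**The plan's own figure.** The 21 cannot be reproduced because no SD is given. Solving backwards with a noncentral t (df 20), 80% power at n = 21 requires a paired standardised difference dz = 0.643. If the 5% is a paired mean difference, the SD of the difference is 5/0.643 = 7.8% of the mean. This dz is used throughout. A paired t-test with 22 women then has 82.0% power.

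**Does the AUC already adjust for time zero?** Barely. In a 0–180 min trapezoidal AUC, time zero gets half of the first 15-min interval: 7.5/180 = 4.2% of the weight.

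**Variance with the covariate.** The one-way repeated-measures ANOVA has (22 − 1)(3 − 1) = 42 error df; the covariate leaves 41. The variance of a meal contrast is multiplied by about (1 − r²)(1 + 1/40), where 1/40 is the cost of estimating the slope.

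| r | Variance ratio | SE ratio (square root) | Equivalent unadjusted n = 22/ratio |
|---|---|---|---|
| 0 | 1.025 | 1.012 | 21.5 |
| 0.3 | 0.933 | 0.966 | 23.6 |
| 0.5 | 0.769 | 0.877 | 28.6 |
| 0.6 | 0.656 | 0.810 | 33.5 |

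The simulated mean SE ratios were 1.012, 0.966, 0.877 and 0.810. The ratio equals 1 at r² = 1 − 1/1.025 = 0.024, so r is about 0.16.

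**Power with 22 women** (simulation, 100,000 runs per r):

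| Test | Unadjusted | r = 0 | r = 0.3 | r = 0.5 | r = 0.6 |
|---|---|---|---|---|---|
| Three-meal omnibus, one meal differing from the other two | 86% | 85% | 89% | 94% | 97% |
| One uncorrected pairwise contrast, three-meal model | 84% | 83% | 86% | 92% | 95% |
| Paired two-meal ANCOVA (df 20) | 82% | 80% | 83% | 90% | 94% |

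Power breaks even between r = 0.15 and 0.2 with three meals, and between 0.2 and 0.25 for the paired version. Type I error at r = 0.5 was 0.050 for the pairwise and omnibus tests, with and without the covariate.

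**If the AUC is baseline-subtracted.** Let k be the ratio of within-person SDs, baseline to time-averaged AUC. Subtraction multiplies the variance by 1 + k² − 2rk, which is below 1 only when r > k/2. With k = 1 (assumed), this is 2 − 2r: 1.4 at r = 0.3 and 1.0 at r = 0.5. Simulated pairwise power:

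| r | Subtracted, k = 0.5 | k = 0.75 | k = 1 | k = 1.5 | Covariate, any k |
|---|---|---|---|---|---|
| 0.3 | 86% | 80% | 70% | 49% | 86% |
| 0.5 | 93% | 90% | 84% | 61% | 92% |

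Once the covariate is in the model, subtracting the baseline changes only its slope, not the meal contrast. In one simulated data set the contrast (SE) without the covariate was 3.76 (2.29) for total and 6.41 (1.84) for subtracted AUC. With it, both gave 5.66 (1.80).

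**The case against.** The strongest objection is that the gain rests on a correlation the documents do not give. Between r = 0 and 0.3 the pairwise change is only −1 to +2 points. Gains of 8 points or more need r of 0.5 or higher, and nothing in the plan supports such values. The evening meal, the fast and the fixed cycle phase are aimed at exactly this variation. This stands as a limit on the size: the gain may be small or nil. It does not remove the case, because the cost is small and the possible gain larger.

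The link between the one-way ANOVA and the AUC is also inferred from adjacent sentences. That is fair, but it is the natural reading: the AUC gives one value per meal, and the time-by-meal analysis is introduced separately as an addition.

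If the AUC is baseline-subtracted, the baseline is already used, and when k is small subtraction performs about as well as the covariate. That stands too, but the plan does not say which AUC is meant, and subtraction can do much worse when k is larger. The time-by-meal ANOVA may include time zero, but it does not adjust the AUC comparison.

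Finally, the planned ANOVA is valid, the unadjusted power of 82–86% already exceeds the stated target under this calibration, and the study is concluded. All true, so this is an improvement in efficiency and not a correction of an error. The recommended model has no period term, but neither does the planned ANOVA, so this does not favour one over the other.

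**Conclusion.** The concern holds. A baseline collected at every visit is not used as a covariate in the comparison of a primary outcome, and precision may be lost as a result. Under the calibration to 80% power at 21 participants, adjustment costs 1 to 2 points of power at r = 0. It gains about 8 points at r = 0.5 and 11 to 12 at r = 0.6, with break-even at r of roughly 0.15 to 0.25. The SE of a three-meal contrast falls by 3%, 12% and 19% at r = 0.3, 0.5 and 0.6. These figures rest on an unknown r, two-sided testing and equal variances and correlations across meals. Confidence in the omission is high; confidence in the size of the benefit is moderate. The validity of the planned test is not in question.

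**What to change.** In section 4.2, define the appetite AUC as total rather than baseline-subtracted, with its start time and units. Compare meals in a within-person mixed model containing meal, that visit's time-zero score on the same scale, and the participant's mean time-zero score, so that the slope for the visit's score is estimated within persons. Report the unadjusted AUC comparison alongside. Do not substitute simple subtraction, which loses precision when r < k/2.

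Leave the time-by-meal ANOVA as planned. Moving time zero out of it has a real cost, because section 4.2 runs post hoc tests only after a significant interaction. In a simulation with one meal raised by a constant 1 SD from 15 to 180 min and independent residuals (20,000 runs), the interaction was significant in 58% of runs with time zero as a level and 5% without. With serially correlated residuals (AR(1), 0.5 or 0.7; 4,000 runs) the figures were about 69% against 7% and 81% against 9%, so the direction holds but the sizes do not generalise. If time zero were used there as a covariate instead of a level, the post hoc trigger would have to include the meal main effect.

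The cost is one or two degrees of freedom and no new data. Section 4.1 describes a concluded study, so unless the adjustment was fixed before the data were seen, it must be labelled as an added analysis.

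### For appetite AUC and lunch intake, section 4.2 as written gives only a three-meal omnibus ANOVA, which cannot by itself show a kefir effect; the LGI-Kefir versus LGI-Milk contrast is not named

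*Combined protocol and SAP*

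**What the plan says.** Section 2 sets the aim: whether kefir benefits appetite and later food intake when taken with low- or high-GI meals. Section 3.3 lists three crossover meals (LGI-Milk, LGI-Kefir, HGI-Kefir) and states: "The primary outcomes were appetite sensations and subsequent food intake".

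Section 4.2 reduces serial appetite ratings to one number per session: "Postprandial appetite sensations were quantified as area under the curve (AUC) calculated according to the trapezoidal rule". The next sentence gives the test: "One-way (1-factor) analysis of variance (ANOVA) for repeated measures was applied to determine statistical differences between groups". It then adds a two-factor (time x meal) repeated-measures ANOVA and says that "Bonferroni post hoc tests were applied to significant time x" meal interactions. The significance rule is general: "For all statistical analyses, p values less than 0.05 were considered to have statistical significance".

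Lunch intake is also one measurement per session. Section 3.5 says that "any remaining food was reweighed to determine intake at lunch". The serial ratings do have a time factor, since by section 3.3 the "appetite scale was applied at 15, 30, 60, 90, 120, 150 and 180 min" as well as at baseline.

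Neither section 4.1, section 4.2 nor any other section names a comparison of LGI-Kefir with LGI-Milk. Section 4.1 refers to a 5% difference between groups without saying which meals.

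**The concern.** The aim is a kefir effect. The one-way ANOVA asks something else: whether any of the three meals differs from the others. The interaction-triggered Bonferroni tests cannot supply the missing comparison for AUC or lunch intake, because neither has an interaction with time to test.

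This matters because the third meal was built to differ strongly in GI. A GI or composition effect with no kefir effect at all could produce a significant three-meal F. A reader following section 4.2 literally would then have a significant primary result and no stated analysis to show whether kefir was responsible.

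**Working it through.** **1. Which pair isolates kefir.** Differences between the meal totals in Table 1 (section 3.4):

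| Pair | kcal | Av. carbohydrate (g) | Protein (g) | Fat (g) | GI |
|---|---|---|---|---|---|
| LGI-Kefir − LGI-Milk | 444 − 443 = +1 | 54.0 − 53.9 = +0.1 | 17.9 − 17.9 = 0.0 | 16.6 − 17.1 = −0.5 | 41 − 40 = +1 |
| HGI-Kefir − LGI-Kefir | 447 − 444 = +3 | 75.8 − 54.0 = +21.8 | 14.5 − 17.9 = −3.4 | 7.9 − 16.6 = −8.7 | 70 − 41 = +29 |
| HGI-Kefir − LGI-Milk | 447 − 443 = +4 | 75.8 − 53.9 = +21.9 | 14.5 − 17.9 = −3.4 | 7.9 − 17.1 = −9.2 | 70 − 40 = +30 |

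Only the first pair is matched on macronutrients and GI as well as energy. There is no HGI-Milk meal, so no contrast isolates kefir at high GI.

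**2. The plan's own figure.** Section 4.1 states 21 participants for 80% power to detect a 5% difference. It gives no SD, test, sidedness or pair of meals, so 21 cannot be reproduced. I solved backwards instead. For a two-sided paired t-test at 0.05 with n = 21 and 80% power, the standardised paired difference (dz, mean difference divided by the SD of differences) is 0.643. That implies an SD of differences of 5 / 0.643 = 7.8% of the mean. This is an assumption, not a recovered input. A one-sided test would give 0.56, and sizing on the omnibus test would give 0.609.

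**3. Omnibus power at n = 22 (section 3.1).** Under sphericity, the noncentrality of the three-level repeated-measures F is λ = n Σ(μ − μ̄)² / σ², where σ² is half the variance of a paired difference. If one meal alone is shifted by δ, Σ(μ − μ̄)² = (2/3)δ², so λ = (4/3) n dz² = (4/3)(22)(0.643²) = 12.1, on 2 and 42 degrees of freedom. Power is 0.862, and λ is the same whichever meal is shifted.

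**4. Kefir contrast at n = 22.** The paired t noncentrality is dz√n = 0.643 × √22 = 3.02. Two-sided power at 0.05 is 0.820 if LGI-Milk differs, and 0.05 if it does not.

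**5. Results.** Simulation of 40,000 crossovers per scenario agrees with these calculations.

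| Assumed dz | Omnibus significant (either case) | Kefir contrast, only HGI-Kefir differs | Kefir contrast, only LGI-Milk differs |
|---|---|---|---|
| 0.4 | 45% | 5% | 43% |
| 0.64 | 86% | 5% | 82% |
| 0.8 | 97% | 5% | 95% |

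At dz 0.64 with only HGI-Kefir different, about 94% of the significant omnibus results come with a non-significant kefir contrast (0.81 / 0.858).

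**6. Wider range.** If the SD of differences is 5%, 10%, 15% or 20% of the mean, the kefir contrast has 99%, 61%, 32% or 20% power for a 5% difference at n = 22.

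**The case against.** The strongest reply is that this is silence, not a wrong statement. Section 4.2 does not list the outcomes for the one-way ANOVA and does not exclude pairwise follow-up. A short plan written in the past tense may leave out routine comparisons, and section 3.4 lets an informed reader identify the matched pair. This stands as far as it goes: the documents do not show that only an omnibus test was run, and a reader should not infer that. They do show that post hoc testing is mentioned only for the interaction, and that the comparison which answers the aim is never named.

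The equality of 86% and 86% is also conditional. It follows from the symmetry of the F test for equal-sized shifts under sphericity. If the HGI-Kefir shift is half as large, the omnibus is significant in 30% of trials. The figures illustrate the attribution problem and do not estimate this trial's error rate. The logical point needs none of them.

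The serial ratings partly cover the gap, since Bonferroni tests can compare meals at single time points, but only after a significant interaction. A meal difference that is constant over time produces no interaction, and lunch intake is never reached.

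Finally, a reader might infer that gating on the omnibus loses much power. It does not: within one outcome, power for the kefir pair at dz 0.64 is 78% gated, against 82% as a single planned contrast.

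**Conclusion.** The point holds for appetite AUC and lunch intake. On the natural reading of section 4.2, their stated test does not answer the aim in section 2, because a significant F across three meals does not separate a kefir effect from a GI or composition effect. The size depends on assumptions that the plan does not supply (dz, equal-sized shifts, sphericity). The attribution gap rests only on Table 1 and the wording of section 4.2.

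Two stronger readings are not supported. One is that the trial cannot test kefir: it can, within the low-GI meals, with one paired contrast on data already collected. The other is that the missing contrast calls for a multiplicity correction across the primary outcomes. That is a separate question with a real power cost, and section 3.3 does not define the outcome family precisely enough to count it.

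**What to change.** Add to section 4.2, in two or three sentences:

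- For each appetite AUC and for lunch intake, LGI-Kefir minus LGI-Milk is the contrast that tests kefir. Report the within-participant difference with its 95% CI and p-value whatever the omnibus result. The composite score can follow the same rule and keep the status that section 3.6 gives it.
- HGI-Kefir versus LGI-Kefir is reported as a GI and composition contrast.
- Conclusions about kefir are limited to the low-GI meal.

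The existing one-way and time x meal ANOVAs stay. Section 4.1 describes the study as concluded with 22 participants, so if the data have already been analysed the contrast should be labelled as not pre-specified.

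No new data are needed and no analysis is removed. Naming one contrast costs no power: 82% at dz 0.64, against 66% if all three pairs were Bonferroni-adjusted.
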